4.3.4 Study Endpoint (Visit 19/Week 16)

- Subjects to complete the health-related quality of life survey, the Medical Outcomes Study 36 item Short Form (SF-36v2™) health survey.
- Vital signs will be obtained and recorded.
- The ulcer will be assessed – visual inspection – complete ulcer characteristics form (see appendix). Determine if reaches 100% epithelization determined by clinician.
- Labs drawn from each subject, hematological and chemistry panel. Pregnancy test of childbearing age.
- If concern for infection, confirmatory bacterial culture will be obtained (deep swab culturette or tissue specimen/biopsy). Radiographical x-rays and blood work (CBC, ESR, CRP, and Chem) may also be performed if deemed necessary by investigator clinician.
- Digital imaging of ulcer location, if remains non-healing then 2 images to be obtained prior to and after surgical debridement.
- Surgical debridement of ulcer if not healed, will be performed using curette or blade and standard therapy.
- Changes in concomitant medications, adverse events, compliance to offloading, will be recorded.

4.3.5 Follow-Up Phase (Visits 20 to 23/Weeks 17 to 28)

- The ulcer will be assessed – visual inspection – complete ulcer characteristics form (see appendix). Determine if reaches 100% epithelization by clinician.
- Digital imaging of ulcer location, if remains non-healing then 2 images to be obtained prior to and after surgical debridement.
- Surgical debridement of ulcer if not healed, will be performed using curette or blade and standard therapy.
- Changes in concomitant medications, adverse events, compliance to offloading, will be recorded.

5 ADVERSE EVENTS

All adverse events reported spontaneously by the subject/or in response to questioning or observation by the investigator will be recorded.

Reporting of Adverse Events:

The Investigator will be responsible for assessing the relationship of the adverse event to the investigational product, and the seriousness and expectedness of the adverse event at the time of occurrence. All adverse events that occur during the trial will be documented.

AE's/SAE's reported during the study, or SAE's reported within 30 days of the end of the study, should be followed to resolution of the AE/SAE or, within thirty days from the end of the study, a further and final assessment of the outcome should be made. Each AE will be categorized as "serious" or "not serious" based on the definition of an SAE. An SAE is defined as an AE resulting in at least one of the outcomes described in the sections below.

The severity of AEs will be classified as "mild", "moderate", or "severe", based on the following definitions:

- Mild: Awareness of sign, symptom, or event, but easily tolerated; does not interfere with usual daily activities or tasks.
- Moderate: Discomfort enough to cause interference with usual daily activity; may warrant therapeutic intervention.
- Severe: Incapacitating; inability to perform usual activities and daily tasks; significantly affects clinical status; requires therapeutic intervention.

Adverse events will be assigned a relationship (causality) to the study products. The Investigator will be responsible for determining the relationship between an AE and the study product. The type of event, organ system affected, and timing of onset of the event will be factors in assessing the likelihood that an AE is related to the treatment. Relationship of AEs to study products will be classified as follows:

- Not Related: No relationship exists between the AE and the treatment. The event is attributed to a pre-existing medical condition or an intercurrent event unrelated to the study product.
- Possibly Related: Follows the treatment, but may have developed as a result of an underlying clinical condition or treatments/interventions unrelated to the study product.
- Probably Related: Follows the treatment, but is unlikely to have developed as a result of the subject's underlying clinical condition or other treatment or other interventions.
- Definitely Related: Follows the treatment and physical evidence shows a convincing relationship to the treatment.
- Unknown: Follows the treatment, but unable to determine the relationship to the treatment.

Subject Follow-up:

Subjects who experience an AE will be followed until the AE has resolved, if possible.

Serious Adverse Events:

A serious AE (SAE) will be defined as any untoward medical occurrence that occur after signing the informed consent until the Final Evaluation that:

- Results in death,
- Is life-threatening,
- Requires inpatient hospitalization or prolongation of existing hospitalization,
- Results in persistent or significant disability/incapacity,

- Is a congenital anomaly/birth defect,
- Other (event not covered by SAE categories but in the investigator's opinion, should be considered serious).

Important medical events that may not result in death, be immediately life threatening, or require hospitalization may be considered an SAE when, based upon medical judgment, they may jeopardize the subject and require intervention to prevent one of the outcomes listed above.

Reporting Serious Adverse Events:

The Investigator must report all SAEs (including any subject deaths) occurring during the study (from informed consent until the Final Evaluation). Once the Investigator becomes aware of an SAE, he/she must e-mail (preferred method of communication) or telephone the IRB within 24 hours.

A written report must follow within 48 hours of the time the Investigator learned of the event. This written report must include a full description of the event and all supporting documentation available at that time (e.g., lab reports, electrocardiogram [ECG] reports, etc.). Additional follow-up information must be reported to the Sponsor on the appropriate form as it becomes available and/or upon Sponsor request.

Data Safety Monitoring Board:

Since this is an open-label trial, no data safety monitoring board will be established.

Stopping Criteria:

The emerging clinical and safety data will be reviewed during the trial, and as a result of this review it may be necessary to terminate the study before all patients have completed the protocol. In such circumstances subjects will be followed up for safety assessment.

6 STATISTICAL DESIGN

Measures:

Measures will be collected at baseline, weekly thereafter, with primary endpoint of complete healing at Week 12, and final secondary endpoint measurement at Week 20. The ulcer will be assessed weekly and will be treated as described above. A designated inter-observer will be at each of the testing sites, (blinded to the treatment of the subjects) which will perform all measurements. The following measurements will be taken: size (surface area calculation), photos (digital includes ruler) and complete foot ulcer assessment (description of ulcer/characteristics), before and after debridement. Subjects where ulceration healed earlier than Week 12 will have follow-up assessment one week after healing, then at Week 12 and 20. If ulcerations healed after 12 weeks, then the subjects will be assessed at one week after healing and at Week 20. There will be 4 follow-up visits (Weeks 17, 20, 24, 28), assessed every 4 weeks for a total of 16 weeks.

During the study, if ulceration appears to be infected as determined by clinical presentation characterized by the presence of two or more signs of inflammation,³ the clinician will follow the protocol of obtaining wound culture for microbiology, radiographs, blood work (CBC, chemistry panel, sedimentation rate, and C-reactive protein), and treatment immediately with appropriate antibiotics. Subjects with infected ulcers will be withdrawn from study and investigators will be notified. In addition, adverse events will be well documented and treated per protocol, and subjects will be withdrawn from study.

Clinical Outcomes:

- The percentage of subjects that have complete closure of ulceration by Week 12 and Week 20. Complete healing will be defined as full re-epithelialization with no drainage, or callus formation and remains closed after 1 week of wound closure.
- Rate of wound healing to achieve complete closure. Weekly measurements of surface area will be recorded on a grid marked acetate sheet, using a metric ruler to determine length and width of the wound.
- A diabetic foot ulcer assessment form will be filled out at weekly follow-up visits, that describes characteristics of ulceration including peri-ulcer erythema, wound margins, fibrin, granular tissue, peri-ulcer pruritus, edema and location, pain, amount of drainage and type, amount of epithelialization, pain level, depth, and bioburden.
- Number of incident subjects with infection, osteomyelitis and acute Charcot during the study, will be withdrawn from the study.
- Number of incidence of adverse effects will be reported from all sites, and will be withdrawn from the study.
- Veterans' Short Form Health Survey (SF-36v2TM), a self-administered questionnaire will be used to measure quality of life, given at beginning and at the end of the study.
- EuroQol Questionnaire (EQ-5D) to evaluate overall quality of life and to facilitate the calculation of health utilities and quality adjusted life years (QALYs). The EuroQol questionnaire (EQ-5D) will be administered at beginning and at the end of the study.

Sample Size Estimation:

The sample size was estimated based on 80 percent power, significance level 0.05, to detect a difference in the incidence of ulcer closure of the two study groups and the standard of care group (Stplan4.3).⁴ It is expected that 50% of the Dermagraft® and Oasis® groups will reach complete ulcer closure by Week 12 and approximately 25% closure with those subjects that received the standard of care (numbers based on previous studies as described previously). We would expect the difference to be 25% between the standard and the treatment group. By using a Chi-square test without continuity correction test would require 57 subjects in each group. If we estimate the difference to be 20% and lower of the cure rates to be 30%, then we would require 88 patients in each group.

Analyses:

The primary end point is wound closure by Week 12, which will be analyzed using Chi-square test to compare the percentages of subjects with complete closure in each group. We will also perform exploratory analysis with logistic regression, using the complete closure at 12 weeks as the dependent variable and the independent variables would include, treatment, size of ulcer, location on foot, how long ulcer has been present, previous revascularization (will analyze as subset group), offloading compliance, concomitant medications, foot deformity, history of amputation, diabetes complications index, and glucose control (HbA1c). Selection of covariates will be performed by stepwise modeling procedures.

We will perform a cost-effectiveness analysis comparing the treatment groups Dermagraft®, Oasis® and the standard care group at the NCHCS using ANOVA or Kruskal-Wallis test depending if data is normally distributed for comparison of the three treatment arms. If significant, we will further analyze with pair-wise comparisons by using t-test or Wilcoxon rank-sum test with the Bonferroni correction to control for type I experiment-wise error rate of 0.05. A p-value less than $0.05/3 = 0.0167$ will be considered statistically significant.

We will evaluate the cost-effectiveness of the Oasis® compared to Dermagraft® and the standard of care by measuring QALYs as the measure of effectiveness, based on results obtained from SF-36v2™ questionnaire. Multiple regression will be used to allow to evaluate continuous dependent variable outcomes, including change scores between baseline and end of study physical (PCS) and mental (MCS) component summaries from the SF-36v2™ questionnaire.

Rates of healing among the three groups will be analyzed using log-rank test to compare time of healing within 20 weeks among the 3 treatment groups.

Secondary endpoint (complete healing at 20 weeks), recurrence ulceration rate at 20 weeks will be analyzed using Chi-square tests. In addition, demographics, smoking history, and characteristics of the wound will also be summarized in table. Data that are continuous variables will be summarized by using mean, median, standard deviation, coefficient of variation, minimum and maximal values. Frequency tables will summarize categorical variables.

Timeline and Milestones:

Months	Year 1		Year 2	
	1-6	7-12	1-6	7-12
Aim 1: Recruitment				
Step 1: Screening (2-week run-in phase)	✓	✓	✓	
Step 2: Randomization/Assignment	✓	✓	✓	
Aim 2: Data Collection				
Step 1: Healed by Week 12	✓	✓	✓	✓
Step 2: Wound not healed by Week 12, continue in study until Week 20	✓	✓	✓	✓
Step 3: If wound has not reached closure beyond the 8 weeks of Dermagraft® – will switch to standard of care (expensive). Oasis® – continue to the end of study	✓	✓	✓	✓
Aim 3: Data Analysis				
Step 1: Outcome effectiveness If outcome show significant difference will cross over for intent-to-treat	✓	✓	✓	✓

7 References

1. Vista/CPRS data record system from 2006-2008, retrieved on 4/7/2009.
2. Vista/CPRS data record system from 2006-2008, retrieved on 4/7/2009.

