4.3 STUDY FLOW CHART

Study Plan Schematic

Procedure	Visit 1 (Week -2)	Visit 2 (Week -1)	Visit 3 (Week 0) Randomization	Visits 4-10 (Week 1-7) Treatment	Visits 11-18 (Week 8-15) Treatment	Visit 19 (Week 16) Study Endpoint	Visits 20-23 (Week 17-28) Follow-Up
Informed Consent	X						
Inclusion/Exclusion Criteria	X	X	X				
Physical Exam	X					X	
Vital Signs	X	X	X	X	X	X	
Ankle-Brachial Index	X						
Fungal Infection Culture and Malignancy Evaluation	X						
Blood Sample Drawn for Labs	X						
SF-36v2™, EQ-5D, QALYs Questionnaires	X						Visit 20 only
Ulcer Assessment	X	X	X	X	X	X	X
Debridement	X	X	X	X	X	X	X
Ulcer Photography and Area Measurement	X	X	X	X	X	X	X
Randomization			X				
Dermagraft® Tx + SOC			X	X			
Oasis® Tx + SOC			X	X			
SOC	X	X	X	X	X	X	X
Concomitant Medications	X	X	X	X	X	X	X
Adverse Events	X	X	X	X	X	X	X

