- Changes in concomitant medications, adverse events, compliance to offloading, will be recorded.
- If ulcers heal sooner than 8 weeks, the subject will be assessed the following week. Ulcer healing is defined by 100% epithelization as determined by the clinician. The subject with healed ulcer will also return for follow-up visits Weeks 9, 16, 20.

NOTE: if ulceration remains open after 8th application – then will switch back to standard of care therapy (if budget allows, may consider extending graft course).

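### The only post-baseline SF-36v2 and EQ-5D is dated three ways (Week 16, Week 17, end of study), and the visit schedules for healed subjects do not name Week 17, so quality-of-life data could go missing according to healing

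*Combined protocol and SAP*

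**What the plan says.** Questionnaire timing appears in three places.

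- The flow chart (Section 4.3) has one row, "SF-36v2™, EQ-5D, QALYs Questionnaires", marked at Visit 1 and then at Visit 20 alone. The table of contents dates Visit 20 to Week 17. The row makes no distinction by healing status.
- Section 4.3.4 (Visit 19, Week 16) lists the SF-36v2: "Subjects to complete the health-related quality of life survey, the Medical Outcomes Study 36 item Short Form (SF-36v2™) health survey". It does not list the EQ-5D.
- Section 6, Clinical Outcomes, says the EQ-5D "will be administered at beginning and at the end of the study", and says much the same of the SF-36v2. No week is given.

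Visits for healed subjects also appear in three places.

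- Section 6, Measures, for closure before Week 12: "Subjects where ulceration healed earlier than Week 12 will have follow-up assessment one week after healing, then at Week 12 and 20". For later closure: "If ulcerations healed after 12 weeks, then the subjects will be assessed at one week after healing and at Week 20".
- The next sentence of that paragraph: "There will be 4 follow-up visits (Weeks 17, 20, 24, 28), assessed every 4 weeks for a total of 16 weeks". It does not say whether healed subjects are included.
- Section 4.3.3: "If ulcers heal sooner than 8 weeks, the subject will be assessed the following week", and then "The subject with healed ulcer will also return for follow-up visits Weeks 9, 16, 20".

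The analyses that need the second questionnaire are the QALYs and the PCS and MCS change scores. Section 6 names the EQ-5D as the route to QALYs under Clinical Outcomes, but bases them on the SF-36v2 under Analyses. Neither the protocol nor the SAP says how a subject without a second questionnaire is handled.

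**The concern.** A change score or QALY here rests on a single post-baseline reading. If attendance at that reading depends on whether the ulcer has closed, the missing data are determined by the primary outcome. Closure is expected to be twice as common in the graft arms as in standard care, so the missingness would differ by arm. Those left with a second reading would be mainly subjects with open ulcers. A complete-case comparison of graft with standard care would then understate any quality-of-life gain that comes from closure, and that gain is what the cost-effectiveness analysis is meant to value.

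**Working it through.** **Inputs.** Section 6, Sample Size Estimation: closure by Week 12 of 50% (Dermagraft), 50% (Oasis) and 25% (standard care), with 57 per arm and 171 in total. The visit weeks are those set out above.

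**The plan's own figure.** For 50% versus 25%, 80% power, two-sided 0.05 (sidedness assumed) and no continuity correction:
n = [1.960·√(2·0.375·0.625) + 0.842·√(0.25 + 0.1875)]² / 0.25² = 57.7 per arm. The arcsine form gives 57.3. The stated 57 is reproduced to within rounding and is not in dispute; it serves only to size the effect.

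**Who reaches a questionnaire visit if only the healed-subject schedules are followed**

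| Week of closure | Week 16 (SF-36v2) | Week 17 (SF-36v2 and EQ-5D) |
|---|---|---|
| Before 8 | Yes under Section 4.3.3, no under Section 6 | No |
| 8 to 14 | No | No |
| 15 | Yes (the one-week check) | No |
| 16 | Yes (still on regular visits) | Yes (the one-week check) |
| 17 or later | Yes | Yes |

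If the Section 6 follow-up sentence covers everyone, Week 17 is scheduled for every row.

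**Numbers healed by Week 12.** 28.5 + 28.5 + 14.25 = 71.25 of 171 (41.7%).

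**Assumptions for the size of the effect.** The documents give no distribution of healing times. Assume constant weekly hazards: −ln(0.50)/12 = 0.0578 (graft) and −ln(0.75)/12 = 0.0240 (standard). Assume also that the score differs by a fixed amount d between closed and open ulcers, and that only subjects with a second reading are analysed. The proportion still open at week t is then 0.50^(t/12) for graft and 0.75^(t/12) for standard care.

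**Reading A: everyone attends Week 17.** None missing by schedule; loss 0%.

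**Reading B: SF-36v2 at Week 16, with Section 4.3.3 returning those closed before Week 8 (taken as by Week 7).**
- Missing (closed in Weeks 8 to 14): graft 0.667 − 0.445 = 22.2%; standard 0.845 − 0.715 = 13.1%. Total 57 × (0.222 + 0.222 + 0.131) = about 33 of 171 (19%).
- Closed by Week 16: 60.3% and 31.9%; true contrast 0.285d.
- Closed among those observed: (0.603 − 0.222)/(1 − 0.222) = 49.0% and (0.319 − 0.131)/(1 − 0.131) = 21.6%; observed contrast 0.274d.
- Loss: 1 − 0.274/0.285 = about 4%.

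**Reading C: Week 17 under the strict Section 6 healed schedule.**
- Missing (closed by Week 15): 58.0% and 30.2%, or 33.0 + 33.0 + 17.2 = about 83 of 171 (49%).
- Closed by Week 17: 62.5% and 33.5%; true contrast 0.291d.
- Among those open at Week 15, closed by Week 17: 10.9% and 4.7%; observed contrast 0.062d.
- Loss: 1 − 0.062/0.291 = about 79%.

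**Oasis versus Dermagraft.** At 50% and 50% the missing fraction is the same in both arms under every reading and the expected contrast is zero, so no differential bias follows at the planned rates.

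**The case against.** A reader might infer that Week 17 is missing from the Section 6 schedule, that healed subjects therefore have no scorable QALY or PCS/MCS change, and that the 79% is the expected loss. The documents do not support this, for four reasons.

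- The follow-up sentence in Section 6 lists Week 17 and does not exclude healed subjects.
- Sections 4.3.4 and 4.3.5 make the paired images and the debridement conditional on the ulcer still being open. That presumes some attendees at Week 16 and at Weeks 17 to 28 are healed.
- Section 6 gives both instruments at the end of study with no exemption. The healed-subject sentences follow a description of ulcer measurements and do not mention questionnaires.
- Section 4.3.3 brings early healers back at Week 16, where Section 4.3.4 gives the SF-36v2. Those subjects have a PCS/MCS change and, since the analysis text derives QALYs from the SF-36v2, a QALY as well.

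These points stand, and they remove the claim that data must be lost. They do not remove the ambiguity. If everyone attends Weeks 17 to 28, naming Week 20 separately for healed subjects is redundant. The follow-up sentence is also inconsistent in itself: Weeks 17 to 28 span 11 weeks, not 16, and Weeks 17 and 20 are three weeks apart, not four. End of study does not settle it either. Section 4.3.4 labels Week 16 the study endpoint, Section 6 puts the final secondary measurement at Week 20, and follow-up runs to Week 28. A site could reasonably act on the specific rule for healed subjects, and under that rule no dated post-baseline EQ-5D visit is named.

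It is also fair to say that the secondary outcome named in the protocol summary compares Oasis with Dermagraft, where the effect is small. The Section 6 cost-effectiveness analysis nevertheless includes the standard-care arm.

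**Conclusion.** The point holds as a contradiction in timing that carries a risk of outcome-related missing data. It does not show that such data will be lost. The questionnaire week and the healed-subject visits each have more than one answer in the documents, and some combinations leave healed subjects without a second EQ-5D (closure by about Week 15) or SF-36v2 (closure in about Weeks 8 to 14). The loss in the graft-versus-standard contrast is 0% if all attend Week 17, about 4% for the Week 16 SF-36v2 and about 79% on the strictest Week 17 reading. The last figure is a worst case. The 4% and 79% rest on the planned closure rates, constant hazards, a fixed difference d and a complete-case analysis. The primary endpoint is untouched. The change is worth making because the inconsistency is easily removed and bears on a stated secondary objective.

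**What to change.** Give both the SF-36v2 and the EQ-5D to every randomised subject, healed or not, at Week 20 (Visit 21). That is the late visit common to the flow chart and both healed-subject schedules, and Section 6 already uses it for the final secondary endpoint. Specifically:

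- change the flow-chart entry from Visit 20 to Visit 21;
- move the SF-36v2 item in Section 4.3.4 to the same visit and add the EQ-5D;
- define end of study as Week 20 for the QALY and PCS/MCS analyses;
- reconcile the healed-subject visits in Sections 4.3.3 and 6 with the Section 6 follow-up sentence, and say whether that sentence applies to healed subjects.

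Confirming that all subjects attend a single visit at Week 16 or Week 17 for both instruments would also close the gap, but it would mean altering the healed-subject schedules. The Week 20 option needs only amended wording and adds no visit. Its cost is that the quality-of-life reading falls 3 to 4 weeks later than now written.

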Each subject will be given a unique identifier that will have no personal information linked after assignment of a randomly computer generated list of three repeated numbers which will be available for each site. The request for assignment will be emailed to the Data Coordinator with a completed eligibility form, and no personal identifiers except for initials and a last 4 digits of social security. The Data Manager will assign a number and the next sequential group assignment with each subsequent request will be placed in sealed envelopes. Subject demographics will not be provided until this assignment is complete. Participants will be randomly placed into the standard therapy, Oasis® or Dermagraft® groups. There will be an estimated of 57 patients in each group.

The patients will not be informed of treatment administered. However, due to the handling of the Dermagraft® (packaging and thawing), whereas Oasis® is readily available at room

temperature, the Investigator/clinician will be able to identify the two treatments. Therefore, to avoid assessment bias, we will have an Inter-observer that will be blinded to treatment to perform all follow-up wound evaluations and record measurements. Following measurement/wound assessment, the treatment will be performed by another assigned clinician, which will not the involvement of the Inter-observer.

Withdrawal:

The subjects may withdraw from the study at any time during the study, upon request. The investigator may also discontinue a subject if it is determined that the subject has not responded to therapy or adverse event occurred, which requires alternative therapy. Those subjects that have undergone treatment will be followed and documented until end of the study. If there is more than 10 percent loss to follow-up, then investigators will attempt to recruit additional subjects.

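### Section 6 requires withdrawal for infection or adverse events, Section 3 does not, and no analysis set or missing-status rule keeps these subjects in the Week 12 closure comparison

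*Combined protocol and SAP*

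**What the plan says.** Section 6 (Measures) states the rule for infection, "Subjects with infected ulcers will be withdrawn from study and investigators will be notified", and continues that "adverse events will be well documented and treated per protocol, and subjects will be withdrawn from study", with no limit by seriousness or relatedness. Section 6 (Clinical Outcomes) repeats it in two garbled bullets: "Number of incident subjects with infection, osteomyelitis and acute Charcot during the study, will be withdrawn from the study" and "Number of incidence of adverse effects will be reported from all sites, and will be withdrawn from the study". The first of these is the only place where osteomyelitis and acute Charcot lead to withdrawal.

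Section 3 (Withdrawal) reads differently. On the investigator's discretion it says "may also discontinue a subject if it is determined that the subject has not responded to therapy or adverse event occurred, which requires alternative therapy", and on follow-up it says "Those subjects that have undergone treatment will be followed and documented until end of the study". Subjects can also leave by choice ("The subjects may withdraw from the study at any time during the study, upon request"). Losses can trigger further recruitment: "If there is more than 10 percent loss to follow-up, then investigators will attempt to recruit additional subjects".

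The primary analysis, in Section 6 and again in the SAP, is a chi-square test on the percentage closed by Week 12 in each group. Week 20 closure is also tested by chi-square, and time to healing by log-rank. Neither place defines an analysis population, a denominator, a rule for missing status or a censoring rule. Intent-to-treat appears once, in a Timeline and Milestones line about crossing over, and that line defines no population.

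**The concern.** Ulcer infection and non-response are plausibly linked to failure to close. If they end participation before Week 12 and the subject is then left out of the percentage, failures leave the denominator and the closure rate rises. The between-arm difference can then be enlarged, reduced or created, depending on how many leave each arm.

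The trial is meant to support replacing an expensive product with a cheaper one, so false similarity between Dermagraft and Oasis would be as damaging as a false difference. With no rule fixed in advance, two statisticians could follow this plan and use different denominators, and the choice could be made after the results are known.

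**Working it through.** **Passages side by side**

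- Section 6 (Measures and Clinical Outcomes): withdrawal is mandatory for infection and adverse events, and in Clinical Outcomes also for osteomyelitis and acute Charcot.
- Section 3 (Withdrawal): discontinuation is optional, limited to non-response or an adverse event needing other therapy, and treated subjects are followed to the end. This is the direct conflict.
- Sections 4.3.3 and 4.3.4 describe the work-up of suspected infection and do not mention withdrawal. Section 5 follows adverse events to resolution where possible. These are silent or compatible, not contradictory.
- Healed-subject visits: Weeks 9, 16 and 20 in Section 4.3.3; one week after healing, then Weeks 12 and 20, in Section 6. A Week 12 assessment is therefore not consistently scheduled.

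**The plan's own figure**

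Inputs from Section 6: closure 50% vs 25%, significance level 0.05, power 80%, chi-square without continuity correction. Two-sided testing is assumed, because sidedness is not stated and a one-sided test would need 46 per arm. With p̄ = 0.375:

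n = [1.96·√(2·0.375·0.625) + 0.842·√(0.25·0.75 + 0.50·0.50)]² / 0.25² = 57.7

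The arcsine form gives 57.3. The stated 57 per arm reproduces, and power at 57 is 79.5%.

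**Effect of dropping withdrawn subjects**

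Let p be true closure among all randomised, w the share withdrawn, and f the closure rate of withdrawn subjects relative to their arm (0 = none close, 1 = unrelated to closure). Then:

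- dropped: observed rate = p(1 − wf)/(1 − w), with n = 57(1 − w)
- counted as not closed: observed rate = p(1 − wf), with n = 57

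Rejection rates use the normal approximation to the pairwise two-sided 0.05 chi-square. The only documented rate is about 20% overall dropout (Section 3), which is not tied to infection. All rates by arm, and f, are assumptions.

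(i) *Planned comparison, equal withdrawal.* w = 20% in each arm, f = 0: 0.50/0.80 = 62.5% and 0.25/0.80 = 31.3%. The difference is 31 points instead of 25, and power is 86% with 45.6 per arm.

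(ii) *Planned comparison, unequal withdrawal, f = 0.* With 5% active and 20% standard care withdrawn: 52.6% − 31.3% = 21 points. With 20% active and 5% standard care: 62.5% − 26.3% = 36 points.

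(iii) *Two products truly at 50%, 10% vs 20% withdrawn (51.3 vs 45.6 subjects left).*

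| f | Observed rates | False difference | Type I error |
|---|---|---|---|
| 0 | 55.6% vs 62.5% | 6.9 points | 10.6% |
| 0.5 | 52.8% vs 56.3% | 3.5 points | 6.3% |
| 1 | 50% vs 50% | 0 | 5.0% |

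For f = 0 the standard errors are 0.1002 (null) and 0.0998 (alternative), so the rejection rate is Φ((0.0694 − 1.96·0.1002)/0.0998) + Φ((−0.0694 − 1.96·0.1002)/0.0998) = 0.106. With 20% withdrawn from both of two equal products there is no false difference.

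**Effect of counting them as not closed**

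For the subjects in (iii): f = 0 gives no difference; f = 0.5 gives 47.5% vs 45.0% (2.5 points, 5.8%); f = 1 gives 45% vs 40% (5.0 points, 8.4%). With 20% unrelated loss in each arm, 50% vs 25% becomes 40% vs 20%, a difference of 20 points with power 64.8%. Observed-only analysis keeps 25 points with power 70.0%.

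**Log-rank**

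For case (iii) with f = 0, simulated type I error was about 6% whether subjects were censored at withdrawal or kept at risk. The effect there is small.

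**The case against.** The strongest defence is that Section 3 is the dedicated withdrawal text and promises follow-up of treated subjects. Withdrawn may then mean off study treatment only, with Week 12 status still collected. The percentage of subjects closed in each group also reads naturally as a percentage of those randomised. This is a fair reading and would remove most of the harm. It does not settle the matter: no section says that withdrawn means off treatment only, and none says that follow-up data after withdrawal enter the primary analysis.

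A second objection is that bias needs a chain of conditions: follow-up stops, subjects are dropped, and withdrawal is related to non-closure. For a false difference between equal products, withdrawal must also differ between arms. None of these is documented. This stands as a limit on the size of the problem. But equal withdrawal is enough to inflate the planned active-versus-standard difference, as (i) shows.

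A reader might infer more than the documents support:

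- That the plan excludes withdrawn subjects. It does not say so; it says nothing either way.
- That Sections 4.3.3, 4.3.4 and 5 also contradict the withdrawal rule. Not mentioning withdrawal, or following an adverse event to resolution, can coexist with it.
- That the log-rank comparison is seriously biased. The simulations do not show that; the gap there is the unstated censoring rule.

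**Conclusion.** The concern holds in this form: the mandatory rule in Section 6 conflicts with the discretionary rule and continued follow-up in Section 3, and nothing in Section 6 or the SAP fixes who is analysed or how a missing status is counted. Followed literally, the rule can remove outcome-related failures from the primary comparison, so this is more than a missing detail.

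The size is not known. Under the assumed rates, dropping withdrawn subjects turns a true 25-point difference into anything from 21 to 36 points, and type I error between equal products lies between 5.0% and 10.6% in case (iii). The upper figure assumes that every withdrawn subject is a non-closer. If withdrawal is unrelated to closure, only precision is lost. These are illustrations, not predictions for this trial.

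**What to change.** 1. Reconcile Section 3 (Withdrawal) with Section 6 (Measures and Clinical Outcomes) and define withdrawn, so that stopping study treatment does not end outcome collection. Collect Week 12 and Week 20 ulcer status for every randomised subject who does not withdraw consent, and align the healed-subject visits in Section 4.3.3 with those in Section 6. No view is given on when treatment should stop.
2. State in Section 6 and the SAP that the primary analysis includes all randomised subjects in their assigned arm, including those lost before any additional recruitment, using observed status whenever it exists.
3. Fix in advance one rule for subjects still without status, whatever the reason. Counting a subject with no confirmed closure as not closed is one example. Report an observed-only analysis beside it, because neither is neutral. Counting unrelated losses as not closed shrinks a true difference when losses are equal, and creates a false one when they are not (10% vs 20%: 5.0 points, 8.4% type I error). Observed-only is biased when losses are related to closure.
4. State a log-rank censoring rule consistent with step 3. If missing status counts as not closed, that means keeping the subject at risk as unhealed to Week 20.

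The cost is protocol and SAP wording, plus Week 12 and Week 20 visits for subjects who have stopped treatment, some of whom may decline to return. Closure percentages will be lower than if withdrawn subjects were dropped. Under the example rule, power also falls when losses are unrelated to closure: 64.8% against 70.0% for observed-only at 20% loss per arm.
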